### **9. CORRELATIVE/SPECIAL STUDIES**

The rich biology associated with lenalidomide administration in CLL offers the opportunity to perform detailed correlative studies. These studies are outlined below. Outside of studies outlined in [\*\*Section 9.1\*\*](#) which are related to the study primary endpoint, collection times or samples may be deleted or altered (with no excess draws or collection from this baseline) if deemed to be impractical. If this occurs, an amendment will be

submitted related to this but accrual to the study will not be interrupted while this is under review.

Study end points have been met, therefore all research sample collection will cease upon approval of protocol version 24. Given the low number of patients continuing to receive treatment additional research samples will not be of scientific interest.

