Assuming that vaccine success in each arm is binomially distributed, we will use a two-sided chi-square test to compare the difference in proportions. We will constrain the Type I error rate in the comparison of vaccine response rates to 0.10. Using a two-sided test, we will have at least 90% power to detect a difference of 0.40 between the two rates (0.20 vs. 0.60) with a total of 44 evaluable patients (22 in each arm). Comparing these two vaccine success rates, if  $p_A \neq p_B$  and the resulting p-value  $< 0.10$ , we will consider the arm with the higher antibody response rate to have a significantly higher rate of vaccine success than the other arm. This design also allows for an interim analysis to be conducted after 11 patients have been accrued to each treatment arm (i.e. 50% of total planned accrual). Under a Lan-DeMets alpha spending function to constrain the Type I error rate, we will consider it sufficient evidence that one arm has a significantly higher antibody response rate than the other arm if the observed p-value  $< 0.0056$  (design generated using East version 5.3).

Independent of the comparison of vaccine-related efficacy, we will also formally evaluate

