#### **13.4 Sample Size/Accrual Rate**

We expect that at most 10% will potentially drop out prior to administration of the 2nd vaccination, which translates to a total maximum sample size of  $22+2=24$  in each arm for a total of 48 patients. With an anticipated accrual rate of about 3 patients per month, we expect that this trial will be fully accrued in at most 16 months.

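### Section 13.3 keeps the final limit at p<0.10 despite an interim win at p<0.0056, and the named chi-square test has 87.7% power at 22 per arm, not at least 90%

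*Combined protocol and SAP*

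**What the plan says.** All of the design figures are in section 13.3 (Study Design), with the enrolment allowance in section 13.4.

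- Error rate: "We will constrain the Type I error rate in the comparison of vaccine response rates to 0.10".
- Test: "we will use a two-sided chi-square test to compare the difference in proportions".
- Final rule: the arm with the higher response rate is declared better if p<0.10.
- Power: "we will have at least 90% power to detect a difference of 0.40 between the two rates (0.20 vs. 0.60"), with 44 evaluable patients, 22 per arm.
- Interim look: "This design also allows for an interim analysis to be conducted after 11 patients have been accrued to each treatment arm", described as half of planned accrual. One arm may be declared better if the observed p-value is below 0.0056. This limit is set "Under a Lan-DeMets alpha spending function to constrain the Type I error rate", with the remark "design generated using East version 5.3".
- Enrolment (section 13.4): "We expect that at most 10% will potentially drop out prior to administration of the" second vaccination, so the maximum is 22+2=24 per arm.

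The plan does not say which Lan-DeMets function was used, whether 0.0056 is a two-sided or per-tail value, what final limit applies after an interim look, or which variance formula lies behind the power figure.

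**The concern.** A spending function holds the overall error only if the final limit is lowered for the alpha already spent. Here the final limit is the whole 0.10, so the two rules taken together cannot have a nominal error of 0.10.

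The power statement has a similar gap. It is attached to a named test at a stated evaluable number, and that test does not reach the stated figure there.

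Both are design properties that a trial report would be expected to carry over. A reader could not tell from the plan which final limit governs a borderline result.

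**Working it through.** **Inputs (section 13.3):** rates 0.20 and 0.60, 22 evaluable per arm, 1:1 allocation, two-sided alpha 0.10 (z=1.6449), interim at 11 per arm (information fraction 0.5), interim limit 0.0056, final limit 0.10.

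**1. Reproducing the stated power.** Unpooled-variance formula:

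- SE = √[(0.20×0.80 + 0.60×0.40)/22] = √(0.40/22) = 0.1348
- Power = Φ(0.40/0.1348 − 1.6449) = Φ(1.322) = 0.907
- The same formula solved for 90% power gives n=21.4, which rounds up to 22

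So both the 90% and the 22 per arm can be recovered this way.

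**2. Power of the test the plan names.** The chi-square test uses the pooled rate, 0.40, under the null:

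- SE₀ = √(2×0.40×0.60/22) = √(0.48/22) = 0.1477
- Power = Φ[(0.40 − 1.6449×0.1477)/0.1348] = Φ(1.165) = 0.878

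Exact enumeration of all tables with the uncorrected Pearson test at p<0.10:

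| Evaluable per arm | Exact power, 0.20 v 0.60 |
|---|---|
| 22 | 87.7% |
| 23 | 88.9% |
| 24 | 90.6% |

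At 22 per arm, exact power for 0.20 v 0.62 is 90.3%. The arcsine formula gives 87.6%; the continuity-corrected chi-square and Fisher's test give 79.1%. Of the two-sided 0.10 methods tried for 22 per arm, only the unpooled planning formula passes 90%.

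**3. What 0.0056 is.** The O'Brien-Fleming-type Lan-DeMets spend at half information, for 0.05 per tail, is 2×[1 − Φ(1.96/√0.5)] = 0.005575. That matches 0.0056 as a per-tail value, or 0.0111 two-sided. The text, however, compares the observed p-value of a two-sided test with 0.0056, so the plain reading is two-sided. Both are carried forward.

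**4. Nominal overall error.** Interim and final Z are bivariate normal with correlation √0.5. Overall alpha is 1 − P(|Z₁|<c₁ and |Z₂|<c₂).

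| Interim limit (two-sided) | Overall alpha with final 0.10 | Final limit that restores 0.10 |
|---|---|---|
| 0.0056 | 0.1013 | 0.09866 (0.0986 rounded down) |
| 0.0111 | 0.1034 | 0.0965 |

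**5. Exact two-look error.** The 12×12 interim tables were enumerated and the non-stopping ones continued to 22 per arm, for common rates from 0.02 to 0.98 in steps of 0.005.

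| Rule (interim, final) | Peak exact alpha |
|---|---|
| No look, 0.10 | 0.111 |
| 0.0056, 0.10 | 0.112 |
| 0.0056, 0.0986 | 0.112 |
| 0.0111, 0.10 | 0.116 |
| 0.0111, 0.0965 | 0.110 |

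At any common rate, the look adds at most 0.0012 to exact alpha with the 0.0056/0.10 pair, and at most 0.0065 with 0.0111/0.10. Most of the excess over 0.10 comes from the discreteness of the test, not from the interim look.

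**6. Effect on decisions.** At 22 per arm the attainable p-values on either side of 0.10 are 0.0985 and 0.1118. A final limit of 0.0986 therefore gives the same verdicts as 0.10. A limit of 0.0965 does not: 9 v 4 and 18 v 13 responders (p=0.0985) would no longer win. Under 0.20 v 0.60, the chance of an early claim is 17.7% with 0.0056 two-sided and 32.1% with 0.0111. Overall power, with the final limit at 0.10, is 87.7% and 87.9%.

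**The case against.** The strongest reply is that nothing here is a wrong sum. The unpooled formula is a standard planning method and returns the plan's own 22 per arm; with the adjusted group-sequential limits it still gives 90.5% to 90.6%. A gap of 2.3 points is small beside the uncertainty in 0.20 v 0.60. The plan also never aimed for 24 evaluable: it targets 22, replaces patients who leave before the booster, and caps enrolment at 24 per arm.

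On alpha, 0.10 can be read as the rule for a design without a look, since the text only permits one. On the plain reading the corrected limit changes no decision, and the larger figures depend on a per-tail reading that the text does not state. The design output might settle the matter, but it is not in the documents.

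Much of this stands. It limits the size of the problem and rules out calling the 90% a miscalculation. It does not make the power statement true of the chi-square test that the plan names, and it does not supply the missing final limit. Labelling the 90% as an unpooled figure would explain its origin but leave the power of the test at 87.7%, so that is the weaker of the two remedies.

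**Conclusion.** The point holds and is minor. As written, the interim and final limits together give a nominal Type I error of 0.1013, or 0.1034 if 0.0056 is per-tail, against a stated 0.10. The named test has 87.7% power at 22 evaluable per arm, 2.3 points below 90%. It would need 24 evaluable per arm, which equals the maximum enrolment and so leaves no room for drop-out.

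The alpha figures assume that the look is taken at exactly 11 per arm and the final analysis at exactly 22. The power figures assume the uncorrected Pearson test. The O'Brien-Fleming shape is inferred from the numerical match alone.

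**What to change.** In section 13.3:

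- State power as about 88% for 0.20 v 0.60 (90% for 0.20 v 0.62) with 22 evaluable per arm by the two-sided chi-square test. Failing that, say that the 90% comes from an unpooled-variance formula.
- Name the spending function and give the interim and final limits on one two-sided scale, checked against the sponsor's design output. By normal theory the consistent pairs are 0.0056 then about 0.0986, or 0.0111 then about 0.0965.
- Say that the full 0.10 applies at the end only if no interim look was done.

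Section 9 now says "Study end points have been met, therefore all research sample collection will cease upon approval of protocol version 24". If the primary data have been analysed, do not alter the rule. Report instead whether the look took place and which limits were applied.

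The cost is wording only, with no added patients. The stated power becomes slightly less favourable. A final limit of 0.0965 would reverse the 9 v 4 and 18 v 13 results, so it must not be adopted after the data have been seen.

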### 13.3 Study Design

In this trial, patients will be randomized in a 1:1 allocation to receive lenalidomide with PCV13 up front concurrently (Arm A) vs. PCV13 up front and then subsequent administration of lenalidomide (Arm B). In this study we will compare the proportion of patients in each arm who achieve a significant antibody response as defined above. While it is not typical to employ a direct comparison of primary endpoints in the phase II setting, we believe that a randomized phase II design will better control for cohort and sampling variability necessary to assess the primary endpoint. In addition, in a secondary manner, we will also evaluate the clinical efficacy of treatment with lenalidomide in these patients vaccinated with PCV13, where clinical efficacy will be primarily determined through the proportion of patients who achieve a CR within two years (see Analysis Plan for more details).

Randomization will be stratified on exposure to pneumococcal vaccination in the previous 5 years. Those patients who have previously received a polysaccharide pneumococcal vaccine will not be excluded. If a patient drops out of the study prior to administration of a 2nd (booster) pneumococcal vaccination, they will not be considered evaluable for the primary endpoint and will be replaced on the study. However, the patient will be included in analyses of efficacy and tolerability as appropriate.

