clinical efficacy using the two-year CR rate. Previous experience with lenalidomide suggests that late responses may be observed. Therefore, to effectively capture evidence of regimen efficacy (beyond the primary endpoint analysis) we will assess the CR rate in a pooled analysis across both arms since the main component of the regimen is lenalidomide therapy. If we find that one arm has shown to be superior to another in terms of antibody response rate as described above, then we will also compare the CR rates between these two arms in an exploratory manner. For the purposes of this trial, if a patient has a documented CR on at least two consecutive evaluations during the first two years, they will be deemed a clinical success. Given the extended time required to observe this clinical endpoint in these patients, we will use a one-stage design. With 44 patients, we will have at least 90% power and a Type I error of 0.10 to be able to detect a 25% or greater true CR rate versus the null hypothesis that the true CR rate is at most 10%. If 8 or more patients are deemed a clinical success as defined above, then we will consider this evidence of efficacy and worth pursuing further. Otherwise, if at most 7 of these 44 evaluable subjects have a CR at the end of two years of follow-up, then we will consider this insufficient clinical activity and may look to modify the treatment regimen to build on observed vaccine response.

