#### **13.5 Analysis of Secondary Endpoints**

In addition to evaluating the proportion of patients who have a vaccine-related antibody response to PCV13, we will also evaluate the seroconversion rates and antibody titre levels for each of the serotypes of the 13-valent pneumococcal vaccine. These markers will be summarized using descriptive statistics by treatment arm. We will graphically evaluate changes in these serotype-specific markers between the two arms, and we will also use the nonparametric Mann-Whitney rank sum test to compare the geometric mean concentrations.

Secondary endpoints will also include the CR rate following 2 years of lenalidomide treatment. Assuming that the number of CRs is binomially distributed, then we will also generate corresponding 95% confidence intervals for the CR rate estimate. If there is also a significant difference between the arms in terms of the vaccine response to PCV13, then we will also compare the CR rates between the two arms in an exploratory manner, although we will only be able to detect a large differential in CR rates (10% vs. 40%) with at least 80% power and a Type I error rate of 10%. In addition, we will evaluate time to event outcomes such as time to first treatment (TFT) and overall survival (OS). TFT will be defined as the time from study entry to first therapy for progressive CLL as defined by IWCLL 2008 criteria. To evaluate this endpoint, patients will be followed even after discontinuing therapy, where we will document date of subsequent treatment and/or progressive disease. Survival will also be evaluated, although we do not expect

many events in this early stage, asymptomatic group of patients. Time to event outcomes will be summarized and explored between treatment arms using Kaplan-Meier methods. Formal comparison of these endpoints between the two arms will not be done due to lack of statistical power to do so. In a very exploratory manner, we will also assess time to treatment in relation to the results reported by Shanafelt et al (2009); in an exploratory manner, we will utilize their prognostic scoring to identify an expected versus observed time to treatment.[64-65]

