### **13.6.2 Evaluation of response**

All patients included in the study must be assessed for response to treatment, even if there are major protocol treatment deviations or if they are ineligible. Each patient will be assigned one of the following categories: 1) complete response, 2) partial response, 3) stable disease, 4) progressive disease, 5) early death from malignant disease, 6) early death from toxicity, 7) early death because of other cause, or 9) unknown (not assessable, insufficient data). [Note: By arbitrary convention, category 9 usually designates the “unknown” status of any type of data in a clinical database.]

All of the patients who met the eligibility criteria (with the possible exception of those who received no study medication) should be included in the main analysis of the response rate. Patients in response categories 4-9 should be considered to have a treatment failure (disease progression). Thus, an incorrect treatment schedule or drug administration does not result in exclusion from the analysis of the response rate. Precise definitions for categories 4-9 will be protocol specific.

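### Three planning figures for 44 to 48 patients are slightly too favourable, and the complete-response rule has a cut-off for 44 only

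*Combined protocol and SAP*

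**What the plan says.** All references are to the combined protocol and SAP.

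- **Pooled CR test (13.3).** For 44 patients the claim is "we will have at least 90% power and a Type I error of 0.10", the aim being "to be able to detect a 25% or greater true CR rate" against a null rate of at most 10%. The design is one-stage. Eight or more successes count as evidence of efficacy; seven or fewer of the 44 evaluable patients count as insufficient activity.
- **CR comparison between arms (13.5).** This is exploratory and is done only if the vaccine responses differ. The plan says "we will only be able to detect a large differential in CR rates (10% vs. 40%) with at least 80% power", at a Type I error of 10%. It names no test, sidedness or number per arm. The only two-proportion test named elsewhere is the two-sided chi-square test for vaccine response in 13.3, with 22 evaluable patients per arm.
- **Dropout (13.4).** Up to 10% are expected to leave before the second vaccination, "which translates to a total maximum sample size of" 22+2=24 per arm, 48 in all. Section 3.4 gives the accrual range as 44 to 48.
- **Who counts for CR (13.3 and 13.6.2).** Patients lost before the booster are replaced for the primary endpoint. "However, the patient will be included in analyses of efficacy and tolerability as appropriate", says 13.3. Section 13.6.2 adds that eligible patients, with a possible exception for those who took no study medication, "should be included in the main analysis of the response rate".

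**The concern.** Two of these statements promise a minimum power, and a third converts a dropout rate into a maximum sample size. Each can be checked from the plan's own inputs, and each comes out slightly on the favourable side.

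The CR test also has a loose end. Its cut-off and error rates are tied to 44 patients, while the analysis-set wording lets the denominator rise to 48. Section 13.3 calls this a formal evaluation and uses it to decide whether the regimen is worth pursuing or should be modified, so its denominator and operating characteristics ought to be fixed in advance. The reading of any CR difference between arms, and the margin for reaching 44 evaluable patients, rest on the other two figures.

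**Working it through.** **1. Pooled CR rule.** Inputs from 13.3: n = 44, null 0.10, alternative 0.25, success if X ≥ 8.

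A one-sample normal approximation at one-sided 0.10 gives a figure consistent with the claim: Φ[(0.15 − 1.282 × √(0.09/44)) / √(0.1875/44)] = Φ[(0.15 − 1.282 × 0.0452) / 0.0653] = 0.921. The plan does not say how its figure was obtained.

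A fixed cut-off has one exact answer:

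- Type I error: P(X ≥ 8 | 44, 0.10) = 0.068
- Power: P(X ≥ 8 | 44, 0.25) = 0.892

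Other cut-offs at 44 do not help. Seven or more gives Type I error 0.146 (power 0.948); nine or more gives power 0.806 (Type I error 0.028). No cut-off at 44 meets both stated targets.

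**2. CR denominator of 44 to 48.** The 8-or-more rule, assuming every counted patient has the same chance of CR:

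| n | Type I error | Power at 25% |
|---|---|---|
| 44 | 0.068 | 0.892 |
| 45 | 0.076 | 0.906 |
| 46 | 0.084 | 0.918 |
| 47 | 0.093 | 0.929 |
| 48 | 0.102 | 0.939 |

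At 48, nine or more gives 0.046 and 0.881.

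**3. CR comparison between arms.** Inputs: 0.10 v 0.40 and 10% Type I error (13.5). The two-sided chi-square test and 22 per arm (13.3) are assumed to carry over.

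- Pooled formula: Φ[(0.30 − 1.645 × √(2 × 0.25 × 0.75/22)) / √((0.09 + 0.24)/22)] = Φ[(0.30 − 1.645 × 0.1306) / 0.1225] = 0.757
- Unpooled formula: Φ[0.30/0.1225 − 1.645] = 0.789
- Exact enumeration of the chi-square test over all 22 v 22 tables: 0.789
- Exact enumeration at 23 per arm: 0.788; at 24 per arm: 0.805

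**4. Dropout.** Inputs from 13.4: 22 evaluable per arm, dropout of at most 10%, 24 per arm.

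- Loss covered: 2/24 = 8.3%
- Evaluable at 10%: 24 × 0.9 = 21.6 per arm; 48 × 0.9 = 43.2 in total
- Enrolment needed at 10%: 22/0.9 = 24.4, so 25 per arm
- P(at least 44 evaluable of 48): 0.47 at 10% dropout, 0.76 at 7%, 0.91 at 5%

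**The case against.** **The gaps are small, and the comparison between arms is exploratory.** This stands. A power of 89.2% against 90% would change no decision, and the 8-of-44 rule is conservative on Type I error. Section 13.5 gives its 80% as a caution about what can be detected. Section 9 says the endpoints have been met, so restating power cannot alter the design. That sets the weight of the point; it does not make an 'at least' statement true.

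**With 48 in the CR analysis, both power claims are met.** Also true: 93.9% for the pooled rule and 80.5% for the comparison between arms. But 48 is the maximum, not the stated basis, and the pooled claim is expressly for 44.

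**Ten per cent is a ceiling on dropout, and dropouts are replaced.** The ceiling matters: a reader might infer that the trial will probably fall short of 44 evaluable, but the 0.47 holds only at 10%. Replacement does not remove the gap, because 48 caps it.

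Two stronger readings are tempting, and the documents support neither.

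- *That the Type I error claim fails, since it reaches 0.102 at 48.* Section 13.3 ties both the error rate and the cut-off to 44 patients, where the error is 0.068. The 0.102 needs all 48 counted, the cut-off left at 8, and the same CR chance for dropouts as for patients who stay. Arm B patients leaving before the booster have had no lenalidomide, and 13.6.2 allows for excluding patients who took no study medication and counts unknown responses as failures. If four dropouts enter as certain non-responders, the error stays at 0.068.
- *That power for the comparison between arms is far below 80%.* That needs a more conservative test, such as Fisher's, which the plan does not name.

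**Conclusion.** The point holds as a minor correction: three stated figures are wrong as written, each by a little.

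- Pooled CR rule at 44: 89.2% power and 6.8% Type I error, in place of at least 90% and 0.10. This is exact and depends on no choice of method.
- 10% v 40% between arms: about 79% (76% by the pooled formula), in place of at least 80%. This assumes the chi-square test and 22 per arm carry over from the primary comparison.
- Dropout allowance: 24 per arm covers 8.3%, not 10%. The shortfall at exactly 10% is 0.8 of a patient in total (44 − 43.2).

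The missing cut-off for 45 to 48 patients is a gap in specification, not a breach of a stated error rate. The primary analysis method is unaffected; only the margin for reaching its 44 evaluable patients is involved.

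**What to change.** Change the wording in 13.3 to 13.5; no patients are added.

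1. In 13.3, state 89% power and a Type I error of 0.07 for 8 or more CRs in 44.
2. In 13.3, fix the CR denominator in line with 13.6.2, saying how patients who leave before the booster, or before any lenalidomide, are counted. Give the operating characteristics of the 8-or-more rule for each n from 44 to 48, as tabulated above.
3. In 13.5, state about 79% power for 10% v 40%, naming the two-sided 10% chi-square test and 22 per arm.
4. In 13.4, state that 48 patients allow for about 8% dropout (2 of 24 per arm).

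The cost is a few sentences and slightly less favourable stated figures.
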